# 3 Study design and settings

This is a retrospective multicenter study in gynaecology.

Data collection from patients taken care between January 2013 and December 2016, in 10 secondary and tertiary French care centers.

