## 4 Data

Preoperative assessment consists of

- a detailed medical history,
- a urogynecological examination,
- and prolapse quantification by the simplified Pelvic Organ Prolapse Quantification (POP-Q) system (measurement of total vaginal length at rest and points Ba, C/D, and Bp at maximum Valsalva) (11,12).

Anaesthesia type and concomitant surgery are reported.

Perioperative complications are graded using the Clavien-Dindo classification (13) and their management and outcome are described.

Perioperative, early (< 30 days post-operative) and late (> 30 days post-surgery) postoperative symptoms and complications are recorded.

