## 6 Statistical analysis

The primary outcome measure is the perioperative morbidity (up to 30 days after surgery). It comprised the number of patients with bladder wound, ureteral wound, rectum wound, abnormal bleeding requiring blood transfusion, urinary retention, urinary tract infection, hematoma, ureteral complication, second surgery, or fail of procedure.

The secondary outcome is the number of patients with late complications (up to 3 years after surgery). It includes self-catheterization, recurrent urinary tract infections, de novo urinary stress incontinence, chronic pain, vaginal mesh exposure, prolapse recurrence, de novo dyspareunia, secondary surgery, vaginal granuloma, anatomic (Ba point  $\leq -1$ ) and functional failure.

A descriptive analysis of the data will be reported. Median, range, numbers, percentages and confidence intervals were used to describe quantitative and qualitative variables, respectively. Association between demographic and clinical factors (age, body mass index, history of hysterectomy, of POP and stress urinary incontinence surgery, cystocele  $\geq 3$ , concomitant hysterectomy and concomitant sub urethral sling) and perioperative complications will be studied. Bivariate ORs and 95 % confidence intervals will be estimated. Outcomes after surgery with Restorelle® anterior alone or with sling will be compared using a chi-square or a Fisher test.

An alpha level of 0.05 will be used.

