## 7 Number of subjects

The largest users of Restorelle Direct Fix have been selected from all the centers specialized in the management of genital prolapse in France. This series will collect data from the first French installers. This is to obtain a representative sample of at least 100 patients, in accordance with AFNOR NF S94-801 standard (4).

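### Anatomic failure in the late outcome is defined as Ba ≤ −1, which is the well-supported side of the POP-Q scale; the inequality is reversed.

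*Combined protocol and SAP*

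**What the plan says.** Section 6 (Statistical analysis) defines the secondary outcome as a patient count: "The secondary outcome is the number of patients with late complications (up to 3 years after surgery". Its component list includes "prolapse recurrence, de novo dyspareunia, secondary surgery, vaginal granuloma" and ends with "anatomic (Ba point $\leq -1$ ) and functional failure". The parenthesis qualifies the anatomic item, the noun is failure, and the list is of complications. As written, therefore, a Ba of −1 or lower is a failure.

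Section 4 (Data) names the instrument: "prolapse quantification by the simplified Pelvic Organ Prolapse Quantification (POP-Q) system", with "measurement of total vaginal length at rest and points Ba, C/D, and Bp at maximum Valsalva". It lists this under the preoperative assessment. Nothing in the document restates the Ba cut-off in the other direction or presents it as a success criterion.

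For reporting, Section 6 says "Median, range, numbers, percentages and confidence intervals were used to describe quantitative and qualitative variables". It also plans a chi-square or Fisher comparison of outcomes between anterior mesh alone and anterior mesh with a sling.

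**The concern.** Ba is a signed position. On the POP-Q scale −3 is full anterior support, and larger values mean further descent. The document does not print this convention, but it is part of the definition of the measure that Section 4 names. Read against it, the written rule labels the best-supported women as anatomic failures and passes over those with the most descent.

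At stake are the anatomic-failure rate with its confidence interval, and the count of women with any late complication. A woman with Ba = −3 and no other late event would enter that count as a patient with a complication. If the sling comparison covers late outcomes, its direction on this item is at stake too.

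**Working it through.** The plan gives no failure rate and no power figure that rests on this item, so there is nothing to reproduce. The check is to classify Ba values and then follow the consequences under assumed rates.

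**1. Classification**

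| Ba | Written rule (≤ −1) | Reversed, > −1 | Reversed, ≥ −1 |
|---|---|---|---|
| −3, −2.5, −2, −1.5 | failure | not failure | not failure |
| −1 | failure | not failure | failure |
| −0.5, 0, +1, +2, +3 | not failure | failure | failure |

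The written rule disagrees with Ba > −1 at every value. It agrees with Ba ≥ −1 only at exactly −1.

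**2. The anatomic item**

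Let f be the rate of Ba > −1 among women with a postoperative Ba (assumed). The written rule reports 1 − f. For f = 5%, 10%, 20% and 30% it reports 95%, 90%, 80% and 70%.

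Exact (Clopper-Pearson) 95% intervals:

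| Women with Ba | Rate of Ba > −1 | Reported as written |
|---|---|---|
| 100 | 10% (4.9–17.6) | 90% (82.4–95.1) |
| 100 | 30% (21.2–40.0) | 70% (60.0–78.8) |
| 50 | 10% (3.3–21.8) | 90% (78.2–96.7) |
| 25 | 20% (6.8–40.7) | 80% (59.3–93.2) |

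If failure is meant to be Ba > −1, the reported rate is its exact complement. If failure is meant to be Ba ≥ −1 with rate g, and a share b of women lies exactly at −1, the written rule reports 1 − g + b. For g = 20% and b = 0, 5% and 10%, that is 80%, 85% and 90%.

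**3. The late composite**

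Let a be the share of women with a postoperative Ba and r the rate of any other late item. Let rW and rC be the shares of all women who have another late item and also Ba ≤ −1 or Ba > −1, respectively. All are assumed.

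- Written composite = r + a(1 − f) − rW
- Corrected composite (Ba > −1) = r + af − rC
- Difference = a(1 − 2f) − rW + rC

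The constraints are rW ≤ a(1 − f), rC ≤ af and 0 ≤ r − rW − rC ≤ 1 − a. Independence is not assumed; the range covers every possible overlap.

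With all women measured (a = 1), rW + rC = r. Two worked cases:

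- f = 10%, r = 20%: the lowest value has rW = 0.20 and rC = 0, giving 0.80 − 0.20 = +60 points. The highest has rW = rC = 0.10, giving +80.
- f = 30%, r = 50%: the lowest has rW = 0.50 and rC = 0, giving 0.40 − 0.50 = −10. The highest has rC = 0.30 and rW = 0.20, giving +50.

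| f | r | Written minus corrected, points (a = 1) |
|---|---|---|
| 10% | 20% | +60 to +80 |
| 10% | 40% | +40 to +60 |
| 30% | 20% | +20 to +60 |
| 30% | 40% | 0 to +60 |
| 30% | 50% | −10 to +50 |

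With fewer women measured, at r = 20%:

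| f | a = 70% | a = 50% | a = 25% |
|---|---|---|---|
| 10% | +36 to +63 | +20 to +45 | 0 to +22.5 |
| 30% | +8 to +48 | 0 to +35 | −7.5 to +17.5 |

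**4. The sling comparison**

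Replacing an item by its exact complement swaps the two outcome columns of the 2 × 2 table. The two-sided chi-square or Fisher p-value stays the same, but the group with more failures becomes the group with fewer. The composite is not simply complemented, so its p-value could change as well.

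**The case against.** The strongest reply is that the harm depends on literal coding. A swapped symbol, or a success cut-off placed next to the word failure, is a natural explanation, and an anatomic-failure rate of 70–95% would be noticed. That makes the error likely to be caught, but it does not settle the rule. A misplaced success cut-off implies failure at Ba > −1. A flipped symbol implies Ba ≥ −1. The text does not say which, and the neighbouring items of recurrence and functional failure have no stated threshold to fall back on.

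A second reply is that the sign convention is not printed. That is true, but it belongs to the definition of the named scale and is not a result taken from an outside study. A misread symbol is unlikely, because the same section prints a distinct ≥ for the cystocele factor.

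Three stronger readings are tempting and should be resisted.

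- A reader might infer that the composite must be badly inflated whenever most women have a Ba. It need not be. Section 6 lists ten items besides anatomic failure, over three years, so r may be well above 20%. With complete Ba data and f = 30%, the error can be nil at r = 40% and negative at r = 50%. These limits need extreme overlap: under independence at r = 40%, rW = 0.28 and rC = 0.12, and the error is +24 points.
- A reader might infer that women with anterior descent are lost from the late outcome. They are lost only from this item; recurrence, functional failure or another late item may still capture them.
- A reader might infer that the reported rate is always the exact complement of the intended one. It is only if −1 itself is not a failure.

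It is also fair to say that this is one item of a secondary, descriptive outcome.

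**Conclusion.** The criterion is wrong as written and should be fixed. Coded literally, the anatomic item reports 1 − f. That is the exact complement of the intended rate if failure is Ba > −1, and exceeds the complement by the share at exactly −1 if failure is Ba ≥ −1. The direction of the composite error is usually, but not necessarily, upward. Its size depends on the share of women with a postoperative Ba, on f, on the rate of other late items and on their overlap. The document gives none of these, so every magnitude above is an illustration.

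The 30-day primary outcome, the odds ratios for perioperative complications, the other late items reported separately, and the target of "a representative sample of at least 100 patients" are unaffected. The document cannot show that any result has been or will be reported the wrong way round; it shows only that the written rule would produce that.

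**What to change.** Reverse the criterion so that failure is the less-supported side. Write Ba > −1 if ≤ −1 was meant as success, or Ba ≥ −1 if −1 itself is a failure; the sponsor should confirm which. Derive both the anatomic item and the late composite from the corrected rule, and use that rule in the sling comparison if late outcomes are included.

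The cost is one symbol in Section 6, one confirmation and the matching line in whatever code derives the item. The symbol change needs no new data. It does not establish for how many women the item can be derived: Section 4 lists Ba only under the preoperative assessment, and Section 3 states "This is a retrospective multicenter study in gynaecology". The number of women with a postoperative Ba should therefore be reported as the denominator of the anatomic rate.

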# 2 Participants

All adult women who had vaginal repair of pelvic organ prolapse (recurrent or not) planned with anterior Restorelle® Direct Fix™ mesh (with or without posterior mesh) were eligible. Patients are excluded if they did not attend their follow up visit within 30 days of surgery.

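### Cystocele severity enters the risk-factor analysis only as a cut at 3, although preoperative Ba is recorded; under a normal Ba and a linear effect this costs at least about a third of the information

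*Combined protocol and SAP*

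**What the plan says.** Section 4 (Data) describes the preoperative assessment. It includes prolapse quantification by the simplified POP-Q system, with "measurement of total vaginal length at rest and points Ba, C/D, and Bp at maximum Valsalva". Ba is therefore a planned item for every woman. Section 6 also uses it as a number, in the definition of anatomic failure.

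Section 6 (Statistical analysis) then names the candidate risk factors for perioperative complications: "Association between demographic and clinical factors (age, body mass index, history of hysterectomy, of POP and stress urinary incontinence surgery, cystocele" at or above 3, and others. No unit follows the 3, no reason is given for the threshold, and no continuous or trend analysis of severity is mentioned. The method is stated as "Bivariate ORs and 95 % confidence intervals will be estimated", and "An alpha level of 0.05 will be used".

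Section 7 (Number of subjects) aims for a "representative sample of at least 100 patients, in accordance with AFNOR NF S94-801 standard". That number comes from a standard and not from a power calculation.

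**The concern.** A yes/no cut treats all women on the same side of it as identical. If the risk of a perioperative complication changes gradually with the size of the anterior prolapse, the differences within each side are thrown away, although the measurement that would show them has been recorded.

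Two things are at stake. The odds ratio for severity will be less precise than the data allow, in a study whose planned minimum was not chosen with this analysis in mind. A non-significant result for the threshold could then be misread as evidence that severity does not matter. Separately, without a unit the factor is not fully defined. Stage is the natural reading of the 3, but the reader has to supply it.

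**Working it through.** The plan states no power, effect size or precision for this analysis, so there is no figure of its own to reproduce. The check is how much information the cut retains relative to Ba used as measured.

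**Inputs**
- Form of the factor: binary, at or above 3 (Section 6).
- Finer measure available: preoperative Ba (Section 4). Centimetres are inferred, since no unit is printed.
- Number of women: 100, the planned minimum (Section 7).
- Alpha: 0.05 (Section 6), taken as two-sided to match the 95% intervals.
- Share p of women on one side of the cut: not given. Section 2 (Participants) sets no minimum stage; it admits "All adult women who had vaginal repair of pelvic organ prolapse (recurrent or not) planned with anterior" mesh of the study type. A range of 50% to 95% is assumed.
- Event rate: not given. 20% is assumed for the power illustration.

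**Formula.** For a normal covariate with a linear effect on the log odds, the efficiency of a cut relative to the continuous value is φ(z_p)² / [p(1 − p)], where φ is the standard normal density and z_p the normal quantile of p. The loss is 1 minus this.

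Example at p = 0.80: z = 0.842, φ = 0.280, φ² = 0.0784; 0.0784 / 0.16 = 0.490, a loss of 51%.

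| Split at the cut | Retained | Lost | 100 women with the cut equal this many with Ba |
|---|---|---|---|
| 50/50 | 0.637 | 36% | 64 |
| 60/40 | 0.622 | 38% | 62 |
| 70/30 | 0.576 | 42% | 58 |
| 75/25 | 0.539 | 46% | 54 |
| 80/20 | 0.490 | 51% | 49 |
| 90/10 | 0.342 | 66% | 34 |
| 95/5 | 0.224 | 78% | 22 |

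The smallest loss, at a median split, is 1 − 2/π = 36%. The loss reaches 50% at p = 0.79.

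**Sensitivity to the shape of Ba.**
- Uniform covariate: efficiency is 3p(1 − p), so the loss is 25% at 50/50, 37% at 70/30 and 52% at 80/20.
- Ba rounded to whole centimetres and cut at +2 or more (an assumed cut), by simulation: the loss is 34% to 47% when 37% to 77% of women are at or above the cut, 55% at 84%, and 64% to 78% at 89% to 95%.

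**Illustrative power.** Approximate power is Φ(ln OR × √[n e(1 − e) × efficiency] − 1.96), where e is the event rate. Take n = 100, e = 0.20 and an assumed odds ratio of 2.0 per standard deviation of Ba.
- Ba continuous: 0.693 × √16 − 1.96 = 0.81, power 79%.
- Cut at 50/50: 60%. At 70/30: 56%. At 80/20: 49%. At 90/10: 37%.

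**Missing Ba.** If a share f of women have Ba recorded and the category is known for all, the continuous analysis retains about f of the information against the cut's efficiency. It remains the better of the two while f exceeds 0.64 at a 50/50 split, or 0.49 at 80/20, provided that missingness is unrelated to risk.

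**The case against.** The best defence is that a prespecified clinical category gives an odds ratio clinicians can read at once. This cut is also fixed in the plan, so the usual worry about cutpoints picked from the data does not apply to it. If risk really changes at the threshold, the binary factor is close to the right model, and a single straight line in Ba could fit worse. The study is retrospective, and Section 5 (Information for data collection) foresees missing data that must be explained, so Ba may be absent for some women. All of this stands. It is why the remedy needs a linearity check and a count of women with Ba, and why the category should be kept.

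Stronger readings are tempting, but the documents do not support them:
- A reader might infer that the cut discards half or more of the information. That needs about 79% or more of the women on one side. It is plausible that most women planned for anterior mesh lie above the cut, but no distribution is given and Section 2 sets no minimum stage.
- A reader might infer that events will be few and a real gradient will probably be missed. No event rate or effect size is stated, the primary composite has ten components, and 100 is a minimum. In the illustration, power with the cut falls below one half only at about an 80/20 split or beyond.
- A reader might extend the point to age and body mass index. Section 6 lists both without any cut, so no loss can be charged to the plan there. Fixing a unit such as 10 years would only rescale the odds ratio.

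**Conclusion.** The point holds as a minor improvement. The only anatomical severity factor in the association analysis is reduced to a threshold with no stated unit or reason, although a finer measure is a planned data item. With a roughly normal Ba and a linear logit, the loss is at least 36%, and it exceeds half only for splits more lopsided than about 79/21. The uniform case shows that the minimum depends on the shape of the distribution: it is 25% there at a median split. A true step in risk at the threshold would make the loss small.

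The consequence is confined to one factor in an unadjusted, exploratory analysis. The primary outcome, introduced as "The primary outcome measure is the perioperative morbidity (up to 30 days after surgery"), is a descriptive count of patients and does not change.

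**What to change.** In Section 6, replace the threshold as the main form of this factor with wording such as: *The association of perioperative complications with preoperative Ba will be estimated by logistic regression with Ba as a continuous term, reported as an odds ratio per 1 cm with its 95% confidence interval. Linearity on the log-odds scale will be checked, for example by adding a quadratic term. The number of women with Ba available will be reported. Cystocele at or above 3, with its unit or classification stated, will be reported as a secondary descriptive result.*

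The cost is a few lines of plan text and one simple model, with no new data item. There are two downsides: the odds ratio is read per centimetre instead of per severity group, and women without a recorded Ba drop out of that model.

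### The sling versus no-sling comparison in a non-randomised series is unadjusted, so p<0.05 may reflect baseline differences and should not be read as a sling effect

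*Combined protocol and SAP*

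**What the plan says.** Section 3 describes the design: "This is a retrospective multicenter study in gynaecology". Nothing in the document assigns slings at random or says why a sling was or was not placed.

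Section 6 opens its analysis plan with "A descriptive analysis of the data will be reported". It then sets a formal comparison, "Outcomes after surgery with Restorelle® anterior alone or with sling will be compared using a chi-square or a Fisher test", followed by "An alpha level of 0.05 will be used". The outcomes to be compared are not listed.

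Concomitant sling is also one of the factors whose association with perioperative complications will be studied. For these, "Bivariate ORs and 95 % confidence intervals will be estimated". The other factors include age, body mass index, "history of hysterectomy, of POP and stress urinary incontinence surgery", severe cystocele and concomitant hysterectomy. No regression, stratification, matching or caution on interpretation is named anywhere.

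Two related definitions are open. Section 2 admits women "planned with anterior Restorelle® Direct Fix™ mesh (with or without posterior mesh) were eligible", and section 6 does not say where those with posterior mesh fall in the sling comparison. The late outcomes include "de novo urinary stress incontinence, chronic pain, vaginal mesh exposure, prolapse recurrence, de novo dyspareunia", with no denominator given for the two de novo items.

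**The concern.** When treatment groups form by clinical choice, a crude test compares the women as well as the treatment. If women given a sling differ in a factor that also drives complications, the test can reject with no sling effect at all. The plan calls itself descriptive but attaches a hypothesis test and an alpha level, which invites the reader to take p<0.05 as a finding about the sling. The bivariate odds ratios have the same limit and concern the primary outcome. The comparison, with its outcomes unspecified, may also include perioperative morbidity. At stake is a secondary conclusion about adding a sling. The overall morbidity percentage does not depend on this comparison.

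**Working it through.** **What the plan gives.** It gives a crude 2×2 test, alpha 0.05 (sidedness not stated), ten centres and at least 100 patients (section 7). The figure of 100 refers to a standard. No effect size, event rate, power or sling share is stated, so there is no plan figure to reproduce. All rates and splits below are assumptions.

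**Step 1: one unadjusted factor, no true sling effect.** Assume 40 women with sling, 60 without, and a 15% complication risk when the factor is absent.
- Odds without the factor: 0.15/0.85 = 0.176.
- Risk with the factor at odds ratio (OR) 2: 0.353/1.353 = 26.1%. At OR 3: 0.529/1.529 = 34.6%.
- Group risk = prevalence × risk with factor + (1 − prevalence) × 15%.
- For 60% versus 20% at OR 3: sling 0.6×0.346 + 0.4×0.15 = 26.8%; no sling 0.2×0.346 + 0.8×0.15 = 18.9%.
- Crude OR = (0.268/0.732)/(0.189/0.811) = 1.57, although the sling does nothing.

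The rejection probability is the sum of the binomial probabilities of all tables with two-sided p ≤ 0.05 (chi-square without continuity correction):

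| Factor prevalence, sling / no sling | Factor OR | Crude sling OR | Fisher | Chi-square |
|---|---|---|---|---|
| 30% / 30% | 2 | 1.00 | 3.6% | 5.3% |
| 40% / 30% | 2 | 1.08 | 3.9% | 5.7% |
| 50% / 30% | 2 | 1.15 | 4.5% | 6.6% |
| 50% / 20% | 3 | 1.41 | 8.9% | 11.9% |
| 60% / 20% | 3 | 1.57 | 12.9% | 16.3% |

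**Step 2: what adjustment can do.** This is a simulation with 40/60 women, 1,500 replicates and a Firth model with sling plus two listed factors. Rejection is by chi-square before adjustment and by penalised likelihood-ratio test after it.
- Selection only through the two listed factors (each 50% versus 25%, OR 2.5): median sling OR 1.57 becomes 1.02; rejection falls from 18.4% to 3.6%.
- One listed and one unlisted factor at those values: 1.51 becomes 1.24; 17.1% becomes 8.2%.
- Unlisted factor only (60% versus 20%, OR 3): 1.61 becomes 1.59; 16.9% becomes 15.5%.

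Adjustment can therefore remove nearly all, part or almost none of the distortion.

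**Step 3: are there enough events?** With 15% risk when neither factor is present, the first case in step 2 has group risks of 32.2% and 23.2%. Expected events are 40×0.322 + 60×0.232 = 26.8. Under a rule of about 10 events per term (an assumption), three terms need 30 events, and the chance of 30 or more is 27%. In the last row of step 1 the expectation is 40×0.268 + 60×0.189 = 22.1. Thirty events need an event rate of 30% at 100 patients, 20% at 150 or 15% at 200. At the planned minimum, probably only a composite could support such a model.

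**Step 4: the two definitions.**
- *Posterior mesh.* If 40% of the sling group and none of the other group had it, at OR 3, the crude sling OR would be 1.68 and rejection 13.7% (Fisher) or 19.2% (chi-square). At OR 1.5 these are 1.19, 4.5% and 7.3%.
- *De novo items.* Counted over all women, the percentage is (1 − baseline prevalence) × risk among women at risk. At 20% risk and 60% versus 20% baseline prevalence this gives 0.4×20% = 8% against 0.8×20% = 16%. Fisher rejects in 17.7% at 40/60, with equal risk in both groups.

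**Step 5: precision.** With 8/40 versus 12/60, the Newcombe interval for the difference is 0 points (95% CI −15 to +17).

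**The case against.** The strongest reply is that this is a descriptive series making no causal claim about slings, and its size was not set for this comparison. That stands, and it keeps the point secondary. It does not explain why a test and an alpha level are attached.

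The imbalance is also hypothetical. A reader might infer that the groups are known to differ or that the comparison is known to be biased. The documents do not show this: there is no baseline table by sling, and under mild imbalance the error rate is close to nominal.

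Adjustment may have little reach. Step 3 shows that even the case where it works best would usually fall short of 30 events at 100 patients. Baseline stress incontinence, one possible driver of sling use, is not among the listed factors. Both points stand. They argue for a modest model on the composites and plain labelling elsewhere, and against a fixed event threshold or a prescribed order of covariates.

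Two further inferences are tempting but unsupported. One is that the plan builds unequal groups through posterior mesh. The wording reads naturally as anterior mesh alone against anterior mesh plus sling, and nothing states an unequal rule. The other is that de novo percentages are taken over all women. The term ordinarily means that the symptom was absent before surgery. Both need only clarification.

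**Conclusion.** The concern holds in a limited form. The sling comparison and the bivariate odds ratios that include sling are unadjusted in a non-randomised series, so p<0.05 may reflect baseline differences. Under assumed conditions with no sling effect, false rejection runs from near nominal (mild imbalance) to about 13% by Fisher or 16% by chi-square (60% versus 20%, OR 3, 40/60). The true size cannot be derived from the documents. A reader might infer that the primary result is compromised. It is not: the overall perioperative morbidity rate does not use this comparison, and only the factor associations with that outcome share the limit. Adjustment would improve the comparison but cannot be promised to remove the selection.

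**What to change.** In section 6:

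1. Keep the crude table. Report each sling versus no-sling contrast as a difference in percentages with a 95% confidence interval, next to a baseline table by sling group.
2. For the composite perioperative and late outcomes, add a Firth-penalised odds ratio with 95% confidence interval for sling. Adjust it for a small number of factors the section already lists, chosen before the sling table is seen. Let the number of events limit the number of terms. The exact limit and the choice of factors are for the sponsor's statistician.
3. Where events are too few to adjust, give the crude difference and interval without a test-based conclusion about the sling. Label these contrasts and the bivariate odds ratios as unadjusted and exploratory.
4. State that women with posterior mesh are handled by the same rule in both groups. State also that de novo outcomes are counted among women without the symptom before surgery, where the chart records it.

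The cost is SAP wording and a short extra analysis. Baseline symptoms may also have to be extracted from charts, since section 4 does not name them as items. Intervals will be wide at about 100 patients, and confounding will remain if selection for a sling runs through factors not listed.
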